5.0 Study Procedures

5.1 Study Design

- Describe experimental design of the study. Include sequential and/or parallel phases of the study, including durations, and delineate which interventions are standard of care and which are research.
- Include a description of how anticipated risk will be minimized and include an analysis of risk vs. potential benefit.

- Provide description of the study population (delineate all categories of subjects – patients, providers, family members, employees, etc.). Include anticipated enrollment numbers
- Include rationale for including or excluding certain populations – in particular vulnerable populations.
- As applicable, provide information on any added protections for vulnerable populations.
- If applicable include information on data and/or specimen banking to include where the bank is located, who will own the data and/or specimens, and who is overseeing the repository.

The proposed 4-year, multisite, randomized pragmatic trial will assess the real-world application of bCBT for Veterans with anxiety, as delivered by frontline VA PCMHI providers at three facilities (Houston, San Antonio, and New Orleans). Veteran participants will be randomized to bCBT or to Enhanced Usual Care (EUC). EUC participants will receive anxiety education materials, a note in their medical record indicating the presence of elevated anxiety symptoms, and 4 brief monthly check-in calls with project staff. Participants randomized to bCBT will have the option to receive bCBT for anxiety delivered either in person, via VVC-H, or both. The primary outcome, anxiety symptoms, will be evaluated at 4-, 8- and 12-month follow-ups.

Evaluation Framework: For this proposal, we chose a randomized pragmatic effectiveness trial to better align the intervention with standard VA clinical practices. To assess feasibility, acceptability, and preliminary implementation outcomes, we chose the mixed methods RE-AIM Qualitative Evaluation for Systematic Translation (RE-AIM QuEST) framework⁴ that expands on the original RE-AIM framework by highlighting complementary quantitative and qualitative outcomes for each of RE-AIM's 5 elements: Reach (participation rate of the targeted population), Efficacy/Effectiveness (impact of the intervention on outcomes), Adoption (system-level factors associated with intervention use), Implementation (intervention integrity and quality), and Maintenance (continuance of the intervention). Although this study focuses on effectiveness, we will also collect data from Veterans, providers, and VA clinic and operational leaders about the potential for the intervention to be implemented within VA settings.

All randomized participants will receive a note added to their medical charts. The note will provide information about the patient's anxiety symptoms and any actions being taken by the research team. Notes will provide information about the assessment process and will also indicate that the patient should continue to receive care as usual regardless of their study group assignment.

ARM #1: Brief CBT (bCBT):

[figure not shown]
Participants randomized to the bCBT direct referral arm will have their contact information and symptom information obtained from the assessment (e.g. responses from the GAD-7, etc.),

forwarded via encrypted email to a study-consented provider. Provider and clinic personnel will schedule the patient for an initial treatment session. Participants and clinicians will work collaboratively to determine the modality of treatment (i.e., traditional in-person visits, VVC-H, or a mixture). Clinicians will be encouraged to offer 4 weekly treatment sessions but may alter the intensity or "dose" of treatment, based on Veteran anxiety response scores and/or provider/patient decision to discontinue treatment. For completers, the final treatment "dose" may include between 4 and 9 sessions over a course of up to 4 months. Clinicians will be asked to complete the GAD-7 during treatment sessions to assess treatment response (regular GAD-7 administration is consistent with bCBT and measurement-based care). Data on treatment sessions will be documented using template CPRS clinician notes to facilitate clinician documentation, allowing the study team to monitor and extract important treatment information during and after the trial.

Treatment completion will be defined as 4 or more sessions over the 4-month treatment period. A 50% reduction in baseline GAD-7 scores will indicate treatment response^{5,6}. Providers and patients will collaboratively determine whether additional bCBT skill sessions are needed based on treatment response. A 50% reduction in anxiety symptoms was chosen, based on prior work and evidence from other studies^{7,8,9}. This response criterion also appropriately classifies responders with variable baseline anxiety levels.

During active treatment, clinicians will be asked to discuss anxiety symptoms and response with participants as part of the treatment process. Providers will be encouraged to deliver bCBT as long as it remains appropriate for any given patient. If a patient is discovered to have additional needs that make the use of bCBT inappropriate, the clinician can opt to seek additional or alternative care for the patient. The presence of severe depression, substance abuse, and comorbid PTSD could all require the clinician to change or add treatments. At the end of the 4-month treatment period, clinicians will be encouraged but not required to discontinue treatment. For patients who reach the response criterion, clinicians will introduce the potential for treatment discontinuation. For patients who do not reach the targeted anxiety goal by the final session (4th session), clinicians will work with the patient to determine whether additional sessions would be helpful. The provider will have the option to continue care or refer the patient to other therapies that are not a part of the research study based on their clinical judgment.

Figure 1. Response to bCBT and Determination of Treatment Ending

The proposed bCBT intervention (See Appendix 5G) uses a patient-centered approach to increase engagement while addressing the mental health needs of anxious Veterans. A bCBT provider manual and a patient workbook provide structure and increase Veteran participation. The patient workbook will be made available both in hard copy and in an electronic version. The workbook includes intervention session information and worksheets, along with homework assignments to engage Veterans during VVC-H sessions and facilitate between-session activities. The bCBT intervention skill modules use CBT-based techniques established in our prior trials^{10, 11} and flexibly apply these skills to improve anxiety symptoms and overall quality of life (see Table 1). All participants take part in an initial session where they receive psychoeducation on anxiety and the bCBT treatment approach, set goals, and begin self-monitoring. Three core skill sessions focused on relaxation, cognitive, and exposure techniques follow. Participants who do not show treatment response at session 4 will be offered up to 4 additional cognitive and/or exposure skill sessions. All participants receive a final wrap-up session to review gains and plan for maintenance of skills.

Table 1. bCBT Intervention Overview

Session Type	Modules	Content / Description
Session 1	Adapt and Overcome Treatment Overview	Assessment of Veteran concerns, anxiety, worry, and stress; psychoeducation about core symptoms of anxiety; treatment module overview; setting initial goals; self-monitoring
Session 2	Relaxation Skill	Learning How to Relax: Controlling emotional/physical sensations using deep breathing
Session 3	Cognitive Skill	Increasing Helpful Thoughts: Understanding how thoughts affect anxiety; practicing adaptive statements or calming thoughts
Session 4	Exposure Skill	Facing Your Struggles 101: Psychoeducation - avoidance in anxiety; understanding how exposure exercises reduce anxiety; building an exposure hierarchy;
Optional Sessions	Advanced Cognitive Skill	Managing Unhelpful Thoughts: Monitoring and modifying unhelpful thoughts
	Exposure Practice	Facing Your Struggles - Practice: Graduated in-session exposure may include in vivo exposure (for specific fears/worries), interoceptive exposure (for fear of bodily sensations), and/or imaginal exposure (for worry/fears about future outcomes)
Final Session	Wrap-up Session	Review of progress/skills; maintaining changes; addressing barriers

ARM #2: Enhanced Usual Care:

Following randomization, EUC participants will receive educational materials about managing anxiety (see Appendix 9A). These material will be made available to the participant both by mail

and through a weblink. They will also receive a letter encouraging them to discuss treatment options with their VA care providers (see Appendix 9). We will place a note in the participant's electronic medical record notifying his/her PCP and most recent PCMHI provider (if applicable) of the presence of anxiety symptoms. Additionally, EUC participants will receive 4 brief monthly check-in calls from study staff to review the resource list and assess current anxiety symptoms and serve as an attention control (see Appendix 9B for resource list, and Appendix 5H for EUC manual). EUC participants will receive the same study reimbursement as bCBT participants and will be asked to complete the same assessments at 4-, 8-, and 12-month follow-ups. Due to ethical concerns of withholding needed treatment, EUC participants will NOT be restricted from receiving mental health services including psychotherapy during the study period. We fully expect that EUC participants may receive anxiety treatments (e.g., antianxiety and antidepressant medications or psychotherapy).

bCBT Providers:

PCMHI providers who conduct psychotherapy as part of their VA scope of practice will be targeted for recruitment. Providers will not be restricted based on profession. PCMHI clinic directors at all three sites have agreed to support the project and will be the primary points of contact for provider recruitment. PCMHI directors will identify a local champion to further enhance recruitment and communication between the clinical site and study team. Based on the staffing at these sites and rates of provider participation in our prior trials, we expect to enroll 25 providers across the sites.¹⁰ Providers from our recently completed trial included social workers, psychologists, physician assistants, as well as psychology and social work interns and postdoctoral fellows.

bCBT Training:

A tailored training program (See Appendix 5I) will be assigned to each provider based on an initial needs assessment (See Appendix 4A). Tailored training improves relevance, meaning, and motivation while reducing inefficiencies¹². Working with a bCBT trainer ([name] or [name]), each provider will be assigned tailored training elements to complete. All providers will be required to complete the exposure training module. Although the full training program takes 8 hours to complete, providers with prior CBT training and experience will need far less time to complete their program. Most providers in our earlier studies required 3-4 hours to complete training. Providers will be eligible to receive bCBT referrals from the study after completing the training.

Intervention Fidelity:

With the patient's written permission, bCBT sessions will be audio-recorded. Consent for audio recording is not required for participation. Recordings will be uploaded to and maintained on a VA shared drive. These audio-recorded sessions are to be used for training purposes only and will not be placed in the Veteran's medical record. BCBT trainers will assess providers'

adherence and competence using a previously developed standardized rating measure¹³. Rating scores range from 0-8, where 6 is considered "good"^{11,13}. All sessions for each provider's first bCBT patient will be reviewed by a bCBT trainer who will provide feedback to the provider after sessions 2 and 5 (or at the end of treatment). Following review of a provider's first patient, bCBT trainers will review the provider's next 2 exposure sessions as well as 2 randomly selected sessions and will provide feedback to providers on these sessions 2 more times during the first 6 months. If a provider receives a rating of 5 or less on any session, the bCBT provider will review an additional session covering the same skill and provide feedback on this "developmental area". Regardless of ratings, providers will not be removed from the trial, but will receive feedback to address needs. This approach closely resembles that followed in current VA training initiatives.

Minimization of Risk

Veteran Participants:

To maximize confidentiality, participants will receive a unique study number that is attached to study related data. Data will be kept in locked file cabinet housed in a data storage room that has a security keypad as entry. All electronic data files will be maintained within the VA setting and behind the VA firewall. In addition, all electronic data files will be password protected for additional security.

In the event of a participant who reports suicidal ideation during the assessment or treatment process, a specific protocol will be used to triage the participant to the appropriate source of VA care. As part of all baseline and follow-up assessments, study staff will closely monitor and explore all indications of suicidal thinking. The PHQ-9 item #9 asks for responses about thoughts of being "better off dead or hurting yourself in some way". Study staff will follow up on any positive response to this item using a structured crisis assessment protocol (see Appendix 5, Suicidal Ideation Assessment.) The structured assessment will distinguish between passive vs. active suicidal thinking, identify any intent or plans for self-harm, and inquire into family, health care, or community supports (see Appendix 5 for detailed listing of the structured assessment). Participants who express suicidal ideation will be discussed with a study investigator (licensed VA provider) who will triage and refer for care as appropriate. If it is an emergent situation the research assistant will page an on-call licensed practitioner (study PI or co-investigator). The PIs, and other study staff ([name]) are licensed mental health practitioners and will serve as the on-call staff.

Provider Participants:

Prior to any provider recruitment efforts, union representatives at the national level will be notified of the study proposal. Potential therapists will be referred by their clinic director and/or VISN mental health leadership and subsequently screened for appropriateness by the study investigators. The study team will be careful to ensure that VISN leadership or clinic directors do

not require clinicians to engage in this work. Any clinician who does not wish to participate will be excluded. Clinician participants final decision to participate or not will not be made known to their supervisor or VISN leadership. Clinicians who wish to participate (receive the training and provide care) will be enrolled. Therapist information related to performance and feedback will be coded within the study so that no therapist specific information will be identifiable outside of the study itself.

No participants provider nor veteran will be identified in any reports that may be published. Study participants are not required to take any study medication or undergo any invasive procedures; therefore, we do not foresee any study-related adverse events.

Potential Benefits

Veteran Participants:

Participants randomized to the treatment arm will be provided with bCBT while participants randomized to the enhanced usual care arm will receive educational products designed to increase their ability to manage their emotional health issues. Additionally, EUC participants will be encouraged to seek services for their anxiety symptoms. Participants may feel less anxiety, worry, and associated symptoms and may experience an improved ability to perform normal activities of daily life.

Provider Participants:

All clinicians will receive expert bCBT training and ongoing consultation to learn how to apply bCBT in their daily practice.

Analysis of Risk vs. Potential Benefit

The risk-benefit ratio of the study suggests that the proposal is reasonable given the potential direct benefits to participants via the intervention and education provided as well as the potential for this research to benefit other Veterans and the larger research and clinical community by providing detailed information on the use of brief cognitive-behavioral therapy for Veterans.

The potential benefits of the study are numerous, with many involving the provision of care to participants but also including information related to how the VA can improve its ability to train and implement psychotherapies in the primary care setting. Data to be obtained from this study will provide important information on the use of brief cognitive-behavioral therapy for Veterans with anxiety as provided by frontline VA practitioners. Should the intervention prove effective, the study team will target clinical and research initiatives designed to further increase the implementation of these procedures within VA. Risks of the study are minimal and many research participants will be provided with care that may not be available within existing care settings.

Description of study population

Age range of participants:

Young adults (18-21)

Adults (22-65)

Seniors (Over 65)

Veteran Participants:

Veterans with clinically significant symptoms of anxiety defined as GAD-7 total scores of 10 or more at two screening occasions to ensure consistency of anxiety symptoms. The GAD-7 is the current anxiety measure used by VA PCMH clinics and is appropriate for monitoring change in anxiety symptoms over time⁵. Veterans will be excluded only for factors that would render bCBT inappropriate for the PCMH setting: 1) cognitive impairment, 2) presence of bipolar, psychotic or substance use disorders. Veterans currently receiving psychotherapy for anxiety at the time of enrollment WILL be excluded so as not to duplicate services. Veterans receiving antidepressant medications or psychotherapy for conditions other than anxiety at the time of enrollment WILL NOT be excluded.

Provider Participants:

PCMH providers who conduct psychotherapy as part of their VA scope of practice will be targeted for recruitment. Providers will not be restricted based on profession and may include psychologists, social workers, counselors, physician assistants, as well as psychology and social work interns and postdoctoral fellows.

Added protections for vulnerable populations:

No vulnerable populations will be targeted for enrollment, except for VA employees who provide mental health treatment to Veterans. No added protections are planned outside those described above.

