Quantitative data will be collected for 12 months following baseline to allow us to examine the long-term effects of the intervention (see Table 4). An initial telephone assessment will screen for exclusion criteria, with final eligibility determined at the baseline appointment. Four-, eight-, and twelve-month follow-up assessments will be conducted by blinded independent evaluators. Upon completion of the follow-up assessment period, the Veteran will be mailed a Thank You

note (See Appendix 10B) notifying them that their participation in the study is complete and acknowledging their contribution to this research.

Table 4. Assessment Schedule – Effectiveness Aims

	Screen	Baseline	4 mo (post tx)	8 mo F/ U	12 mo F/U
GAD-7	X				
Cog Screen, Demographics, Diversity Supplement, Charlson Index, Attachment, Social Support, Chart Review		X			
MINI – Anxiety, Depression, Mania, Psychosis, Substance use and PTSD modules, Audit-C		X			
GAD-7, OASIS, SF-12V, PCL-5, PHQ-9,		X	X	X	X
Working Alliance Inventory (Patient and Clinician)			X		
Charlson Comorbidity Index – Database Extraction					X
Medication and Health Service Use -- Database Extraction					X

Mixed Methods Exploratory Aim:

We will conduct a mixed-methods formative evaluation (FE), informed by Stetler et al.,³⁵ to evaluate the implementation of the bCBT clinical intervention and VVC-H. The RE-AIM QuEST⁴ framework will inform qualitative and quantitative data collection related to reach, effectiveness, adoption, implementation, and maintenance (see Table 5). We will collect FE data during the study's pre-implementation (Y1 Q1-Q2), implementation (Y1 Q3 – Y3 Q4) and post-implementation (Y4 Q1-4) phases.

Pre-implementation: During pre-implementation, we will conduct semi-structured interviews with the PCMHI clinical director and bCBT champion at each site. Directors and clinical champions will review and provide feedback on the bCBT materials, training materials, provider bCBT delivery procedures, and provider preparedness to deliver exposure in PCMHI. Pre-implementation findings will allow us to refine the bCBT delivery approach, address barriers, and tailor provider support procedures. Consenting of the staff for the pre-implementation interviews will not be warranted as no identifiers will be collected during the interviews.

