6.0 Reporting

- Include procedures for reporting unanticipated problems, serious adverse events, and protocol deviations.
- Include information about whether the study has a Data Monitoring Committee and if so, how often it will meet.

All unanticipated serious adverse events (U-SAEs) and unanticipated serious problems (UAPs) will be reported to the VA Central IRB within five business days. U-SAEs will be reported to VA Central IRB regardless of their relationship to the research. All protocol deviations, violations, and/or noncompliance will be reported to the VA Central IRB within five business days of the reporting individual becoming aware of the occurrence.

Safety information, including SAEs/UAPs, that will be collected:

During completion of the study assessment timepoints the participants mental health will be accessed via questions administered. Participants demonstrating increased mental health distress, based upon responses to the assessment, will be evaluated and referred for additional assessment and intervention as needed. Participants in need of immediate treatment (e.g., active psychosis or suicidal intent) will be referred for appropriate services with VA upon identification. Study staff will follow up on any positive responses to items involving suicidal thinking, using a structured crisis-assessment protocol (see Appendix 5). Participants who express suicidal ideation will be forwarded to a study investigator who will triage and refer for care as appropriate.

All occurrences of events resulting in a participants' death, life threatening experience, hospitalization, prolonged hospitalization, or persistent or significant disability will be documented. Any occurrence of an event that results in the need for medical or other interventions to prevent any of the above listed outcomes will be documented as well. As such, any participants identified as having an immediate mental or physical health issue will be referred to care as appropriate.

Frequency/methods of safety-related data collection:

Collection of safety information will commence when the first participant is enrolled in the study. Safety information may be collected either 1) during baseline and follow up assessments, 2) during bCBT sessions, or 3) during telephone contacts with participants made for purposes of

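### Symptom deterioration is neither defined nor counted by arm, although GAD-7, PHQ-9 and PCL-5 are collected in both arms at every assessment

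*Protocol*

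**What the plan says.** Protocol section 5.1 (Minimization of Risk) gives its reason, "Study participants are not required to take any study medication or undergo any invasive procedures", and concludes: "therefore, we do not foresee any study-related adverse events". Table 1 in the same section describes the treatment. Session 4 introduces exposure and the building of a hierarchy, and among the optional sessions "Graduated in-session exposure may include in vivo exposure", as well as interoceptive and imaginal forms.

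The safety provisions are spread over three sections:

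- **Section 5.5** (Other Demographic and Clinical Data): emergency room visits and hospitalizations are taken from VA data and compared between arms every quarter. Clinical leadership and the IRB are brought in if the arms differ.
- **Section 6.0**: events resulting in death or "life threatening experience, hospitalization, prolonged hospitalization, or persistent or significant disability will be documented", as are events that need intervention to prevent such an outcome. A participant whose answers show increased distress "will be evaluated and referred for additional assessment and intervention as needed". Adverse events are described as having low probability. Local monitoring covers any that are identified, and the DSMB receives annual and semi-annual reports.
- **Sections 5.1, 5.5 and 6.0**: positive answers on suicidal thinking are followed up individually at each assessment.

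Table 4 in section 5.5 schedules "GAD-7, OASIS, SF-12V, PCL-5, PHQ-9" at baseline, 4, 8 and 12 months. Section 5.1 gives EUC participants the same follow-up assessments. Blinded independent evaluators carry out the follow-ups.

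For the arm comparison, section 5.6 and the SAP describe mixed models for anxiety (GAD-7 in the stated aim) and quality of life (SF-12).

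**The concern.** For a psychotherapy with an exposure component, the absence of a drug or procedure does not show that harm is unforeseeable. The relevant harm is that some patients get worse. PTSD and depression are not exclusions in section 5.4, and section 5.1 itself expects that severe depression or comorbid PTSD may lead a clinician to change or add treatment.

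The plan is asymmetric. Benefit has a patient-level definition, a 50% fall in GAD-7. Deterioration has none. The abstract says that the results are meant to support or caution against wider use of such programs, and a caution needs a harm count. Without one, a report of few adverse events would partly reflect what the plan set out to count.

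**Working it through.** **1. What each safety element captures.**

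| Element | Section | By arm? | Captures a scale score that rises without acute care? |
|---|---|---|---|
| Emergency visits, hospitalizations | 5.5 | Yes, quarterly | No |
| Serious events and those needing intervention to prevent them | 6.0 | Not stated | Only if the criteria are met |
| Any identified adverse event, local monitoring | 6.0 | Not stated | Possibly; no definition or tabulation given |
| Increased distress, suicidal ideation | 5.1, 5.5, 6.0 | Not stated | Individual evaluation and referral; no threshold or tally |
| GAD-7 and SF-12 mixed models | 5.6, SAP | Yes | As part of a mean trajectory |
| PHQ-9, PCL-5 scores | 5.5 | No analysis described | Collected, not analyzed |

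No row gives a by-arm count of patients who deteriorate. The responder regression in section 5.6 uses only patients who received bCBT and models improvement.

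**2. Ascertainment outside the assessments.** Section 6.0 names three sources of safety information: the assessments, the bCBT sessions, and calls made to schedule assessments or treatment sessions. It does not name the four monthly EUC check-in calls, although section 5.1 says that those calls assess current anxiety. Events found between assessments may therefore be picked up more often in the bCBT arm, so informal counts could not be compared fairly. Counts from the follow-up assessments are gathered in the same way in both arms.

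**3. Why the mean comparison does not answer the question.** The documents give no deterioration rate and no GAD-7 standard deviation. Assume that 10% of bCBT patients end 5 points worse than the EUC mean, and SD = 5.

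- Patients affected: 0.10 × 145 = 14.5, about 15.
- Shift in the bCBT mean: 0.10 × 5 = 0.5 point.
- Planned effect (section 5.6, d = 0.38): 0.38 × 5 = 1.9 points.
- Gain needed in the other 90% to reach it: (1.9 + 0.5) / 0.9 = 2.67 points.

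The planned effect can thus be reached in full while about 15 patients are worse.

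**4. What a by-arm table could show.** Section 5.6 randomizes 145 and 80 and assumes 25% attrition at one year: 145 × 0.75 = 108.75, about 109, and 80 × 0.75 = 60. The 95% half-width is 1.96 × √(p₁(1−p₁)/109 + p₂(1−p₂)/60), where p₁ is the bCBT rate and p₂ the EUC rate (both assumed).

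| bCBT rate | EUC rate | Half-width (percentage points) |
|---|---|---|
| 5% | 5% | 6.9 |
| 15% | 5% | 8.7 |
| 10% | 10% | 9.5 |
| 5% | 15% | 9.9 |
| 15% | 15% | 11.3 |

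The range is about 7 to 11 points. With 10% against 5%, the half-width is 7.9 and the interval runs from about −3 to +13 points.

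**The case against.** The strongest reply is that safety is already well covered. A reader might infer from section 5.1 that the protocol documents only serious events. It does not: the quarterly by-arm comparison in section 5.5 is not limited to events classed as serious, and section 6.0 extends to events needing preventive intervention and to any identified adverse event. The sentence in section 5.1 does not govern these procedures, so correcting it alone is editorial.

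A reader might also infer that a worsened subgroup would appear in no planned table and no DSMB report. That cannot be established. The documents contain no table shells, and section 6.0 does not itemize the DSMB reports. The fair statement is that deterioration is not named there.

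Nor is worsening invisible. Clinicians use the GAD-7 during treatment sessions, a broad rise in GAD-7 would show in the primary model, and SF-12 is compared by arm. The model fits a line for each participant and residual variances are checked, so a markedly worsened subgroup might widen the spread. None of this is a harm analysis, and none of it covers PHQ-9 or PCL-5.

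Finally, the table would be imprecise: three scales at three visits make nine comparisons, and score rises include ordinary fluctuation. All of this stands. It limits how the table is read, but it does not remove the reason for having one, because the EUC arm supplies the background rate.

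**Conclusion.** The point holds as a gap in definition and analysis, not in data collection. Neither protocol section 5.6 nor the SAP text available defines symptom deterioration, plans a by-arm count of it, or describes a between-arm analysis of PHQ-9 or PCL-5. The listed safety sources are also uneven between arms outside the assessments. Section 5.1 and section 6.0 disagree on whether adverse events are unforeseen or merely unlikely.

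The documents do not show that any real harm would be missed. The 10% rate, the 5-point worsening and the SD of 5 are assumptions that show only how a minority can disappear in a mean. The half-width of about 7 to 11 points rests on assumed rates of 5% to 15%, the planned 25% attrition and a normal approximation. This is a worthwhile, inexpensive improvement and does not threaten the primary analysis.

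**What to change.** In protocol section 6.0 and in the SAP, add one descriptive table by randomized arm for 4, 8 and 12 months. For each of GAD-7, PHQ-9 and PCL-5 it should give:

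- the number assessed;
- the number whose score exceeds their own baseline by a margin that the sponsor fixes for that scale before unblinding, with sensitivity margins on either side (the documents give no figure);
- the risk difference with its 95% confidence interval, preferably a score-type interval because counts may be small (5% of 60 is 3 patients).

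Include the table in the DSMB and final reports. State that it is descriptive, without significance tests, that it covers several scales and visits, and that it includes ordinary score fluctuation. Reword the inference in section 5.1 so that it agrees with section 6.0, and either add the EUC check-in calls to the listed safety sources or state that information from outside the assessments is not comparable between arms.

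The cost is small: no new visit, questionnaire or participant burden, one set of margins to agree, and one table to program. The table will not settle modest differences between arms, and worsening that resolves between assessments would still be missed.
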